8.2.2. Exclusion Criteria

Patients meeting any of the following exclusion criteria will not be included in the study population for analysis:

1. Currently prescribed rimegepant for prevention of migraine or for both the acute treatment & prevention of migraine
2. Rimegepant group: currently prescribed an acute treatment for migraine other than rimegepant
3. Triptan Group: currently prescribed an acute treatment for migraine other than triptans

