8.2.1. Inclusion Criteria

Patients must meet all of the following inclusion criteria to be eligible for inclusion in the final study population for analysis:

1. Patients who have episodic and/or chronic migraine
2. Patients age >18
3. Currently prescribed rimegepant OR triptans for the acute treatment of migraine

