Current comorbidities			Myocardial infarction / Ischaemic stroke / Haemorrhagic stroke / TIA / Cerebrovascular disease / Hypertension / Hypotension / Ischaemic heart disease / Congestive heart failure / Atrial fibrillation / Arrhythmia / Angina / Deep vein thrombosis / Cardiomyopathy / Coronary artery disease / Peripheral vascular disease / Mitral valve disease / Reynaud's disease / Type 1 diabetes (with and without complications) / Type 2 diabetes (with and without complications) / Obesity / Thyroid disease / Hyperlipidaemia / Dyslipidaemia / Mild/Moderate/Severe renal disease / Mild/Moderate/Severe liver disease / NASH / Depression / Anxiety / Stress / Vascular dementia / Alzheimer's disease / Other dementia / Epilepsy / Parkinson's disease / Obsessive compulsive disorder / Panic disorder / Sleeping disorders / Seizures / Vertigo / Chronic pulmonary disease / Asthma / Chronic sinusitis / Connective tissue disease / Hemiplegia/Paraplegia / Rheumatologic disease / Arthritis / Neuropathic pain / Osteoporosis / Neck pain / Back

Table 1. Variables

Variable	Purpose	Data Source(s)	Operational Definition
			pain / Fibromyalgia / Trigeminal neuralgia / Muscle weakness / Any malignancy / Metastatic solid tumour / Tumour without metastases / Gastrointestinal problems / Peptic ulcer disease / Lupus / Anorexia / Alcoholism / Menstrual disorders / IBS / Glaucoma / AIDS/HIV / Erectile dysfunction / Long term effects of COVID-19 / Other / None
Patient received prior acute treatment(s)	Patient current & prior acute treatments	PRF DQ10	Triptan(s) including combinations / NSAID(s) including combinations / Anti-CGRP gepants / Opioid analgesics including combinations / Non-opioid analgesics including combinations / Ergotamines and Derivatives / Serotonin 5-HT1F agonist (ditan) / Other / No drug treatment
Time spent on Rimegepant or triptans (currently receiving)		PRF DQ2a	Days / Don't know
Patient current preventive treatment(s)	Patient current & prior preventive treatment (s)	PRF EQ1 PRF EQ3 PRF EQ10	Yes / No but previously / Never
Patient prior prevention treatment(s)			
Failure to achieve pain freedom within 2 hours post dose (physician perspective)	Outcome-Objective 1	PRF DQ18	Yes / No / Unknown

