8.6. Data Analysis

Analyses will be based on patients receiving rimegepant or triptans only as an acute treatment currently for their migraine.

Data will be stratified by time spent on rimegepant or triptans and number of migraine related headache days.

Analysis will be descriptive. The mean, standard deviation (SD), median, 25th and 75th percentiles and minimum and maximum values will be reported for numeric variables, whilst relative frequencies and percentages will be reported for categorical variables.

The real-world nature of the DSP means many variables will contain missing data. We would expect the base of patients to vary from variable to variable due to imperfect physician knowledge, physicians not wishing to answer the question, etc. The base relevant to each analysis will be reported in any data tables provided. There will be no imputation of missing data. Where missing values are found in a particular variable, any patients with missing values will be removed from all pieces of analysis where that variable is used. However, patients removed from one piece of analysis are still eligible for inclusion in other analyses. In the derivation of PRO variables, the handling of missing data will follow the official instructions as provided by the author/owner of the PRO questionnaire.

Detailed methodology for summary and statistical analyses of data collected in this study is documented in a statistical analysis plan (SAP) below:

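### Does defining rimegepant by product and triptans by class leave the triptan group or its time strata undetermined?

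*Combined protocol and SAP*

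**What the plan says.** Section 8.2.1 admits patients who are "Currently prescribed rimegepant OR triptans for the acute treatment of migraine". Section 8.2.2 then restricts each group to sole use. For one product the wording is "Rimegepant group: currently prescribed an acute treatment for migraine other than rimegepant"; for a class it is "Triptan Group: currently prescribed an acute treatment for migraine other than triptans". The first exclusion in the same list concerns rimegepant alone: "Currently prescribed rimegepant for prevention of migraine or for both the acute treatment & prevention of migraine".

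In Table 1 (Section 8.3) the relevant block is labelled "Patient current & prior acute treatments". It holds two rows. DQ10 covers treatments received before, with a response list that opens "Triptan(s) including combinations / NSAID(s) including combinations". DQ2a covers duration, under the label "Time spent on Rimegepant or triptans (currently receiving" (the parenthesis closes there). In the DQ10 row, Section 8.6.1 pools triptans with triptan combinations. Section 8.6 adds: "Data will be stratified by time spent on rimegepant or triptans and number of migraine related headache days".

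Section 8.5 gives 528 patients for physician-reported outcomes (91 rimegepant, 437 triptans) and 143 for patient-reported outcomes (29 and 113). It also requires all analysis code to be logged.

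**The concern.** A product definition leaves little to interpret, while a class definition raises questions that the plan does not answer in writing. Eligibility turns on what is prescribed now, yet the only treatment-class item listed is about the past. A patient on a triptan combination could be kept, following the DQ10 convention, or removed under a literal reading of the third exclusion. For a patient with two triptans, or one who changed triptan, time on the product and time on the class differ, and time on treatment is one of only two planned stratifiers.

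If analysts resolved these points differently, the same data could give different triptan groups and different strata. The amendment sets triptans beside rimegepant, so a reader might also compare strata that mean different things in the two groups. The patient-reported counts do not add up, which invites the suspicion that group assignment is already unsettled.

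**Working it through.** The plan contains no sample-size or precision calculation to reproduce, so this is mainly a comparison of text, with some arithmetic on scale.

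1. **Item for current prescriptions.** Inclusion 3 and exclusions 2 and 3 all need it, and neither Table 1 nor Section 8.6.1 names it. The rimegepant group needs the same item, so the gap does not come from the class definition. Section 8.2 places the data collection forms in an appendix that is not in the text available here. Section 8.5 already gives counts for both groups, which could not have been produced without a source for current treatment.

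2. **Triptan combinations.** Table 1 lists combinations inside the triptan class, and Section 8.6.1 pools the two. Both statements concern prior treatment. No passage treats a combination as something other than a triptan, so the natural reading carries the same convention to current treatment.

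3. **Two triptans at once.** Membership is clear: such a patient takes nothing outside the class, so exclusion 3 does not apply. Only the duration is open.

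4. **Change of triptan.** DQ2a is labelled as treatment now being received, while earlier drugs belong to DQ10. The label points to the current treatment. Concurrent triptans are the remaining open case, and their number is not given.

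5. **Strata more generally.** Section 8.6 gives no time cut-points for either group, and Section 8.6.1 leaves the unit of DQ2a to choice for both. Stratum assignment is therefore not fully fixed for rimegepant either, and the product/class difference is not the main source of freedom.

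6. **Scale.** Suppose m of n triptan patients are removed. With p_m and p_rest the proportions among those removed and those kept:

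   |p_all − p_rest| = (m/n) × |p_m − p_rest|

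   The share m/n is not in the documents. Assume 2% to 15%, and a 30-point difference between the two sets:
   - 2%: 0.02 × 30 = 0.6 points; group sizes fall from 437 to 428 and from 113 to 111.
   - 15%: 0.15 × 30 = 4.5 points; group sizes fall from 437 to 371 and from 113 to 96.

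   For reference, the 95% half-width of a proportion of 50% is 1.96 × √(0.25/n): 4.7 points at n = 437 and 9.2 points at n = 113.

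7. **Why no safe count follows from this.** The shift can never exceed m/n, so it is tempting to call any m harmless if m/n is below the half-width at 50%. That would give m up to 20 of 437 (20/437 = 4.6 points, below 4.7) and up to 10 of 113 (10/113 = 8.8 points, below 9.2). The comparison fails because the half-width shrinks away from 50%.
   - n = 437, m = 20 with no successes, 375 of 417 in the rest: 375/417 = 89.9%, 375/437 = 85.8%, shift 4.1 points. Half-width at 85.8%: 3.3 points.
   - n = 113, m = 10 with no successes, 93 of 103 in the rest: 93/103 = 90.3%, 93/113 = 82.3%, shift 8.0 points. Half-width at 82.3%: 7.0 points.

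   These are extreme constructions. They show only that no count-based trigger for an extra analysis can be justified this way. The plan itself specifies no intervals or tests.

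8. **Counts.** 91 + 437 = 528, as stated. 29 + 113 = 142, against 143 stated. Nothing in the documents connects the odd patient to combinations or to DQ2a. Section 8.6 has each table report its own base, so the printed total feeds no calculation.

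**The case for a change.** The best case for a change is that the output of a descriptive study is its counts and proportions, so reproducible groups and strata are the least it should offer. The authors evidently considered combinations, since they wrote a rule for prior treatment, and they did not write one for group membership. Logged code records what was done; it does not fix the choice beforehand. Section 8.8 mentions neither the sole-treatment restriction nor the product/class difference. The remedy would cost a few sentences.

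Much of this is accurate. The three details are absent for current treatment, and logging code does not replace a written definition. It does not follow that the plan gives a wrong or unstable answer. Each gap has one sensible reading, supported by the plan's own labels and conventions and open to an analyst who holds the questionnaires. The sole-treatment restriction is disclosed in Sections 8.2.2 and 8.6, so repeating it among the limitations is a matter of preference. The first exclusion names rimegepant because Section 6 describes it as approved for both acute and preventive use; no distortion from that asymmetry has been shown.

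**Conclusion.** No change to the plan is called for. What remains is missing detail: an unnamed source item that both groups need, a combination convention written for prior but not current treatment, and no duration rule for concurrent triptans. No effect on results has been demonstrated, and its direction cannot be given. The 0.6 to 4.5 point range rests wholly on an assumed 2% to 15% share and a 30-point difference, and it concerns overall proportions rather than time strata.

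The conclusion assumes that the physician form records current acute prescriptions, which the reported group counts imply. It also assumes that analysts extend the DQ10 convention to current treatment and read DQ2a as time on the treatment now being taken. It would weaken if many retained patients were on two triptans, which the documents do not let one check. The 143/142 mismatch is a clerical discrepancy of one patient in a fixed-sample descriptive study; correcting it would alter no result.

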8.3. Variables

The variables of interested captured in the data collection forms are summarized in Table 1:

Table 1. Variables			
Variable	Purpose	Data Source(s)	Operational Definition
Physician provided Patient Report Form (PRF)			
Patient age	Patient demographics	PRF AQ1	
Patient biological sex		PRF AQ2	Male, Female, Intersex
Patient BMI		PRF AQ3/4	
Patient ethnicity		PRF AQ6	White / African American / Native American / Asian (Indian subcontinent) / South-East Asian / Asian (other) / Hispanic / Middle Eastern / Other
			Working fulltime / part-time / retirement / student /

Table 1. Variables

Variable	Purpose	Data Source(s)	Operational Definition
Employment Status		PRF AQ8 PRF AQ9 PRF AQ10	unemployed / long-term sick / home maker / don't know Part-time / retirement / student / unemployed / long-term sick due to migraine: yes/no Days off work due to migraine
Insurance Type		PRF AQ14	Medicaid / medicare / commercial / exchange plan / cobra / non-medicare retired benefit / tricare/veterans / other / no insurance / don't know
Migraine diagnosis- chronic? Number of migraine related headache days in last 3 months Severity of attacks over last 3 months Current migraine symptoms/most bothersome symptom Duration of attack without treatment	Patient clinical characteristics	PRF CQ5 PRF CQ4bi PRF CQ7a PRF CQ6a/6b PRF CQ10 PRF CQ3	Yes / No Very mild / Mild / Moderate / Severe / Very Severe Pain on one side of the head / Pain that moves from one side of the head to another/ Pain on both sides of the head at the same time / Pulsating/throbbing pain / Pain worsened by activity / Photophobia / Sensitivity to smell / Visual aura / Light-headedness / Speech changes / Sensory aura / Nausea / Vomiting / Allodynia / Watery/swollen/red eyes / Facial swelling / Runny nose/nasal congestion / Ear congestion / Kinesiophobia / Muscle weakness / Mood changes / Changes in appetite / Other / Unknown Hours/days Tension type headache / Medication overuse headache / Cluster headache / SUNCT /

Table 1. Variables

Variable	Purpose	Data Source(s)	Operational Definition
Other headache conditions			Hemicrania continua / New daily persistent headache / Primary stabbing headache / Primary exercise headache / Primary thunderclap headache / Hypnic headache / Secondary headaches / Other headache conditions / None PRF KQ2/LQ1
Current comorbidities			Myocardial infarction / Ischaemic stroke / Haemorrhagic stroke / TIA / Cerebrovascular disease / Hypertension / Hypotension / Ischaemic heart disease / Congestive heart failure / Atrial fibrillation / Arrhythmia / Angina / Deep vein thrombosis / Cardiomyopathy / Coronary artery disease / Peripheral vascular disease / Mitral valve disease / Reynaud's disease / Type 1 diabetes (with and without complications) / Type 2 diabetes (with and without complications) / Obesity / Thyroid disease / Hyperlipidaemia / Dyslipidaemia / Mild/Moderate/Severe renal disease / Mild/Moderate/Severe liver disease / NASH / Depression / Anxiety / Stress / Vascular dementia / Alzheimer's disease / Other dementia / Epilepsy / Parkinson's disease / Obsessive compulsive disorder / Panic disorder / Sleeping disorders / Seizures / Vertigo / Chronic pulmonary disease / Asthma / Chronic sinusitis / Connective tissue disease / Hemiplegia/Paraplegia / Rheumatologic disease / Arthritis / Neuropathic pain / Osteoporosis / Neck pain / Back

Table 1. Variables

Variable	Purpose	Data Source(s)	Operational Definition
			pain / Fibromyalgia / Trigeminal neuralgia / Muscle weakness / Any malignancy / Metastatic solid tumour / Tumour without metastases / Gastrointestinal problems / Peptic ulcer disease / Lupus / Anorexia / Alcoholism / Menstrual disorders / IBS / Glaucoma / AIDS/HIV / Erectile dysfunction / Long term effects of COVID-19 / Other / None
Patient received prior acute treatment(s)	Patient current & prior acute treatments	PRF DQ10	Triptan(s) including combinations / NSAID(s) including combinations / Anti-CGRP gepants / Opioid analgesics including combinations / Non-opioid analgesics including combinations / Ergotamines and Derivatives / Serotonin 5-HT1F agonist (ditan) / Other / No drug treatment
Time spent on Rimegepant or triptans (currently receiving)		PRF DQ2a	Days / Don't know
Patient current preventive treatment(s)	Patient current & prior preventive treatment (s)	PRF EQ1 PRF EQ3 PRF EQ10	Yes / No but previously / Never
Patient prior prevention treatment(s)			
Failure to achieve pain freedom within 2 hours post dose (physician perspective)	Outcome-Objective 1	PRF DQ18	Yes / No / Unknown
Reason for choice of current acute treatment- 'consistency of response after repeated use' (physician perspective)	Outcome-Objective 1	PRF FQ1a	Complete pain freedom after 2 hours / Pain relief after 2 hours / Relieves most bothersome migraine symptom / Fast onset of action / Relieves even the most severe migraine attacks /

Table 1. Variables

Variable	Purpose	Data Source(s)	Operational Definition
			Prolonged pain relief/long duration of action / Avoids the need for a second dose or rescue treatment / Low headache recurrence (within 24 hours of attack) / Tends to work across all patients / Consistency of response after repeated use / Dual use treatment- a single drug to achieve acute and preventive treatment effects / Ability to prescribe a stronger initial dose, rather than multiple additional doses / Ability to take additional doses for non/partial response / Available as a tablet/capsule / Available as a melt / Available as a patch / Available via nasal administration / Available as an injection / Ability to prescribe for consecutive days (eg, for menstrual migraine and other trigger events / Allows rapid return to function / Patient can continue activities and honour commitments / Patient can enjoy recreational/leisure activities / Reduces number of days missed from school/work / Improves patient's quality of sleep / Patient can maintain relationships / Low risk of medication overuse headaches with repeated use / Lower risk of paraesthesia (abnormal sensation(s) of the skin) / Lower risk of palpitations/flushing / Lower risk of other CV side effects / Lower risk of nausea/vomiting / Lower risk of other GI side effects / Lower risk of memory/concentration problems / Lower risk of drowsiness/sedation / Lower risk of dizziness / Lower risk of fatigue / Lower risk of liver damage / Lower risk of weight

Table 1. Variables

Variable	Purpose	Data Source(s)	Operational Definition
			problems / Lower risk of depression / Lower risk of allergic reaction / Lower risk of breathing difficulties / Lower/no risk of injection site reaction / Lower risk of addiction/abuse / Suitable for adjunctive/add-on therapy / Lack of interaction with other drugs / Safe for long term use / Efficacious in patients who have failed prior acute migraine treatments / Suitable for patients with moderate/high CV risk / Safe in patients with cardiac/circulatory disorders / Suitable for vomiting/nauseous patients / Suitable for patients with menstrual migraine / Suitable for women of child bearing age / Suitable for women of child bearing age / Suitable for physically active patients / Suitable for use in career orientated professionals / Approved for migraine / Good patient adherence / Patient convenience / Patient request/preference for therapy / Cost effective treatment / Persona; experience prescribing this drug / On local/national formulary / Clinical trial/publication evidence / Other selected for rimegepant or triptans
Satisfaction with current acute treatment (physician perspective)	Outcome-Objective 2	PRF IQ1a	Extremely satisfied / Satisfied / Slightly Satisfied / Neither satisfied nor dissatisfied / Slightly dissatisfied / Dissatisfied / Extremely dissatisfied

Table 1. Variables

Variable	Purpose	Data Source(s)	Operational Definition
Drivers for lack of satisfaction with current acute treatment (physician perspective)	Outcome-Objective 2	PRF IQ1b	Lack of efficacy / Slow onset of action / Efficacy diminished over time / Number of side effects experienced / Severity of side effects experienced / Mode of administration / Complicated dosing regimen / The number of prescribed acute treatments / The treatment is costly for the patient / Other
Patient Self-Completion Form (PSC)			
Number of migraine attacks acute treatment achieves pain freedom within 2 hours post dose (patient perspective)	Outcome-Objective 1	PSC HQ6	0 out of every 5 attacks / 1 out of every 5 attacks / 2 out of every 5 attacks / 3 out of every 5 attacks / 4 out of every 5 attacks / 5 out of every 5 attacks
Satisfaction with current acute treatment (patient perspective)	Outcome-Objective 2	PSC HQ18a	Extremely satisfied / Satisfied / Slightly Satisfied / Neither satisfied nor dissatisfied / Slightly dissatisfied / Dissatisfied / Extremely dissatisfied
Drivers for lack of satisfaction with current acute treatment (patient perspective)	Outcome-Objective 2	PSC HQ18b	It only reduces my migraine pain by half / IT reduces my migraine pain by less than half / It does not work quickly enough / It does not work as well as it used to / The number of side effects I experience / The severity of the side effects I experience / I am not happy with the way I have to take it / I find it difficult to know when to take it / I have too many different acute treatments to take / I worry about becoming dependent on it / It costs me too much money / Other
Patient willingness to continue use of acute treatment (patient perspective)	Outcome-Objective 3	PSC HQ18c	Definitely yes / Probably yes / Do not know / Probably not / Definitely not

Table 1. Variables

Variable	Purpose	Data Source(s)	Operational Definition
Migraine Treatment Optimization Questionnaire (m-TOQ6)	Outcome-Objective 4	PSC Section I- m-TOQ6	Reported by item and total score.
When patient takes acute Rx treatment	Outcome – Objective 5	PSC HQ3	Before any sign of a migraine attack, but in anticipation of one starting / At the first sign of a migraine attack (before the pain starts) / When the pain starts / After the pain has started and I have an idea of how severe it is
How many days per month patient takes acute Rx treatment	Outcome – Objective 5	PSC HQ4a	

8.4. Data Sources

Data will be drawn from the Adelphi Migraine DSP, fielding in the US between May and November 2022.

8.5. Study Size

Given the primary research objective is purely descriptive in nature (i.e., no *a priori* hypotheses specified), the available sample size is fixed by the DSP data collection methodology and simply impacts the precision of any estimates. Therefore, formal sample size calculations are not applicable and have not been performed. All patients who meet the eligibility criteria will be included in the study. For this study, the sample size is 528 (91 Rimegepant, 437 Triptans) for the physician-reported outcomes, and 143 (29 Rimegepant, 113 Triptans) for the patient-reported outcomes. Data Management

Pseudoanonymised data are taken from the Migraine VII DSP, which is owned and managed by ARW.

All data analysis will be conducted using Stata 17 software, version 17.0 (StataCorp, College Station, Texas) / IBM® SPSS® Data Collection Survey Reporter v7.5 or the latest available version at time of analysis. All programming code/ syntax written to conduct the required analysis will be logged for transparency and replicability.

